1. BACKGROUND AND JUSTIFICATION

The increasing prevalence of cognitive impairment and dementias, such as Alzheimer's disease, presents a significant challenge to global public health, with rapid intensification concomitant with population aging (United Nations, 2015). The impairment of memory, attention and executive functions that characterize these conditions substantially impacts the quality of life of patients, also exerting a considerable burden on caregivers and health systems.

The term "dementia" encompasses various diseases and conditions that lead to a deterioration in memory, language, problem-solving abilities and other cognitive skills, consequently altering a person's ability to carry out activities of daily living. This global problem affects more than 55 million people, and adds around 10 million new cases annually (World Health Organization, 2023). This constant increase calls for the design, implementation and evaluation of innovative therapeutic strategies to support the care and management of people with dementia and related conditions.

The treatment of dementia is approached from several perspectives, including pharmacological and non-pharmacological interventions. While the former are aimed at managing the cognitive and non-cognitive symptoms of the disease, they do not provide a cure and can cause side effects. On the other hand, non-pharmacological interventions, such as cognitive rehabilitation programs, focus on training and improving cognitive abilities and teaching new strategies and skills to compensate for affected abilities. However, its effectiveness may be limited due to the difficulty of transferring learned skills to everyday contexts, given the artificiality of training environments.

Healthy aging is a key goal for the world's rapidly aging population. As we look for ways to promote cognition and well-being in old age, technology-based interventions have become a popular approach. However, access to and effectiveness of these interventions can be affected by various barriers, such as unfamiliarity with or lack of access to the technology. According to a recent study by Zuschnegg et al. (2023), the results demonstrated that CCIs have a significant effect on memory, working memory, attention/concentration/processing speed and executive function in individuals with mild cognitive impairment, but no significant improvements were observed in global cognition and language. This study also highlighted the need for more research examining the effectiveness of these interventions in more realistic settings, such as participants' homes. This study aims to explore and evaluate the effectiveness of computer-based cognitive interventions (CCIs) in improving memory and cognition in community-dwelling older people, and analyze the barriers and facilitators to the use of CCIs, expanding thus the existing research.

In this scenario, virtual reality (VR) has stood out as a powerful tool for cognitive stimulation in people with cognitive impairment. Its immersive and engaging nature allows it to provide an ecological, safe and controlled environment, in which users can practice cognitive and physical skills in digitally recreated everyday situations. Recent studies support the potential of VR to improve cognitive skills and reduce interference in individuals with mild cognitive impairment (MCI) (Goméz et al., 2022; Papaioannou et al., 2022; Chen et al., 2021; Bauer et al., 2022 al., 2020). A recent meta-analysis and systematic review provides additional evidence by showing a positive impact of VR-based cognitive rehabilitation programs on cognitive and functional outcomes, including improvements in cognitive functions, daily functioning, depressive symptoms, and quality of life (Bitch A . et al., 2023).

For the design of our project, the work of Muñoz et al. (2022) offers a solid foundation on which the "SWOT" matrix and general design guidelines for Human-Computer Interaction (HCI) are provided. These resources are useful to identify strengths, opportunities, weaknesses and

threats of the use of virtual reality technology in cognitive rehabilitation and to optimize the usability of HCI in interventions that use this technology. Furthermore, a recent study conducted by Qiu et al. (2022) supports the acceptability and tolerance of a virtual reality-based cognitive training program in older adults, reflecting that the majority of participants found VR attractive and easy to use, without serious or severe adverse events.

The main objective of this project is to carry out a pilot study to clinically evaluate the effectiveness of virtual reality (VR) sessions in a selected group of 20 patients from the El Carme Socio-Health Center in Badalona. These VR sessions will consist of 360-degree immersive experiences, designed and provided by Reality Telling, that will focus on recreating familiar environments and implementing memory and attention training exercises.

The purpose of these sessions is twofold. On the one hand, we seek to validate the acceptability of these immersive experiences among patients and healthcare professionals, evaluating their willingness to adopt and interact with this innovative form of therapeutic intervention. On the other hand, we propose to examine the impact of immersive experiences in terms of improving cognitive performance, as well as on the commitment and motivation of patients towards their own cognitive rehabilitation process.

3. HYPOTHESIS OR STUDY QUESTION

Main Hypothesis:

The application of a cognitive stimulation program with virtual reality will be well accepted by patients with mild cognitive impairment.

Secondary Hypotheses:

- Virtual reality interventions will be perceived as useful and motivating by patients, promoting positive adherence to the cognitive stimulation program.
- Patients will improve their cognitive performance (attention and memory) on cognitive scales after the sessions.
- Virtual reality interventions will be perceived as useful and applicable as a tool in the clinical practice of cognitive stimulation by healthcare professionals.

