4. GOALS

4.1. Main objective

To evaluate the acceptability of the cognitive stimulation program based on virtual reality among patients with mild or moderate cognitive impairment at the El Carme Socio-Health Center in Badalona.

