5.4 Study variables

5.4.1 Variables result, exposure or effect

Main Outcome Variable:

Acceptability and usability of VR exercises: This will be measured using a user satisfaction questionnaire and the System Usability Scale (SUS). HE will managen after the last session (the eighth).

Secondary Outcome Variables:

Cognitive function (memory and attention), measured through standardized tests: - Specific to attention and memory (Digits, TMT [Annex 3], SDMT [Annex 4]).

- General cognitive function tests:
- Montreal Cognitive Assessment (MoCA) [anexo 5]
- Mini-Mental State Examination (MMSE) [anexo 6]

The evaluations will be carried out before starting the training program and at the end of it (after the eighth session).

Usability of the system by professionals:

This will be evaluated using the System Usability Scale (SUS) for patients and professionals [Annex 7 and 8]. It will be administered to professionals after completing the training program.

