5.7 Statistical analysis

The data collected during the study will be analyzed using statistical methods appropriate for each type of variable. All analyses will be performed using statistical software SPSS 27.0.

Acceptability and Usability: Scores obtained on the System Usability Scale (SUS) will be analyzed descriptively to provide an overall measure of the acceptability and usability of the VR intervention.

Cognitive function: Depending on the normality of the variables, statistical tests will be applied to compare scores (parametric Student's T or non-parametric Wilcoxon (in the case of failure to comply with the assumption of normality).

Demographic and clinical variables: Correlation and multiple regression analyzes will be used to examine relationships between demographic and clinical variables (e.g., age, gender, etiology, education) and changes in acceptability, usability, cognitive function, and quality of life.

The hypotheses will be evaluated at the significance level of p < 0.05 (95% confidence level). As this is a pilot study, the results will be used primarily to generate hypotheses for future research and to provide effect size estimates that may be useful for sample size calculation in future studies.

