6- Physical safety: There is a risk of patients tripping or falling while using VR due to spatial disorientation. To mitigate this risk, patients will be seated during VR sessions and will be

closely supervised by healthcare personnel to ensure their safety. Additionally, the area around the patient will be free of obstacles.

7- Withdrawal effect: If the VR tool is withdrawn after the conclusion of the study, the patients who participated may show less interest in continuing with the conventional cognitive stimulation program. To mitigate this risk, if the results of the study are positive and show significant benefits for patients, a commitment will be made to keep this tool in use within the cognitive stimulation program.

Benefits

1- Cognitive stimulation: VR offers an interactive and attractive medium for cognitive stimulation, which can be more motivating and attractive for patients than traditional therapies.

2- Improved emotional well-being: Patients may experience an improvement in their emotional well-being when participating in immersive VR experiences, especially if the sessions are designed to be enjoyable and fun.

3- Contribution to research: Patients will participate in a study that may contribute to improving the understanding and treatment of cognitive impairment.

To ensure the safety and comfort of participants, healthcare personnel will receive extensive training in the use of VR. All necessary precautions will be taken to minimize risks and participants will be closely monitored for any side effects. It is hoped that participation in the study can have a positive impact on the cognition and emotional well-being of the participants, and that it contributes to research in this field.

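### The main hypothesis falls under the p < 0.05 rule but has only a descriptive analysis, no comparator and no reference value, and early stoppers may drop out of the result

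*Combined protocol and SAP*

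**What the plan says.** The main hypothesis (section 3) is that the VR program "will be well accepted by patients with mild cognitive impairment". The main objective (section 4.1) is "To evaluate the acceptability of the cognitive stimulation program based on virtual reality among patients with mild or moderate cognitive impairment". Neither carries a criterion for success.

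On measurement, section 5.4.1 states: "This will be measured using a user satisfaction questionnaire and the System Usability Scale (SUS"), given after the eighth and last session. The visit table in 5.5 agrees. Section 6.1 instead has participants complete the acceptability and usability questionnaires after each VR session.

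On analysis, section 5.7 states: "Scores obtained on the System Usability Scale (SUS) will be analyzed descriptively to provide an overall measure of the acceptability and usability". It names no analysis for the satisfaction questionnaire. It plans t or Wilcoxon tests for the cognitive scores, and correlation and multiple regression relating demographic and clinical variables to acceptability, among other outcomes. It then adds, without exempting the main hypothesis: "The hypotheses will be evaluated at the significance level of p < 0.05 (95% confidence level"). The next sentence calls the results primarily hypothesis-generating.

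Section 5.2 rules out a control group, and section 5.6 sets 20 patients without a calculation. Annex 7 prints eight simulation items and eight headset items, with no scoring rule, total or cut-off.

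**The concern.** A p-value needs a null value or a comparator, and the plan gives the main hypothesis neither. The level set in 5.7 cannot be applied to the question the study exists to answer. Whether the program was well accepted would be judged once the scores are known, and over a wide middle range of results either answer could be defended.

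The timing of the questionnaire adds to this. If it is given only after session eight, patients who stop earlier contribute nothing to the acceptability result. Some of them will probably have stopped because they did not take to VR, so leaving them out would tend to favour the intervention.

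**Working it through.** **Is there a planned figure to reproduce?** No. The only design figure is n = 20 (5.6), set by the pilot character of the study, resources and expected patient diversity. No effect size, SD, reference, power or precision target is given, so no formula can return 20. Every reference and SD below is an assumption, shown as a range.

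**Can any planned analysis test the main hypothesis?**
- Descriptive scores: no test.
- Comparison between groups: none, because there is no control group.
- One-sample comparison: none, because there is no reference value.
- Correlation and regression: these ask which patients score higher or lower, not whether the level is high. They cannot confirm or refute the hypothesis.

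**How far does the verdict depend on the missing reference?** Suppose 15 of 20 patients accept. The exact one-sided p is P(X ≥ 15), with X binomial(20, p0). For p0 = 50% this is (15504 + 4845 + 1140 + 190 + 20 + 1)/2^20 = 21700/1048576 = 0.021.

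| Assumed reference p0 | Exact one-sided p for 15/20 |
|---|---|
| 40% | 0.0016 |
| 50% | 0.021 |
| 60% | 0.126 |
| 70% | 0.416 |

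**How precise is a proportion with n = 20?** The exact (Clopper-Pearson) limits are the 0.025 quantile of Beta(x, n − x + 1) and the 0.975 quantile of Beta(x + 1, n − x).
- 14/20 (70%): 0.457 to 0.881.
- 15/20 (75%): 0.509 to 0.913.

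An observed 70% is thus compatible with fewer than half of such patients accepting.

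**What would a fixed rule require?** The rule is that the lower limit of the two-sided exact 95% interval exceeds p0.

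| Assumed p0 | Needed | Chance of passing if truth is p0 | If truth is 80% | 90% | 95% |
|---|---|---|---|---|---|
| 50% | 15/20 | 0.0207 | 0.804 | 0.989 | 1.000 (rounded) |
| 60% | 17/20 | 0.0160 | 0.411 | 0.867 | 0.984 |
| 70% | 19/20 | 0.0076 | 0.069 | 0.392 | 0.736 |
| 80% | 20/20 | 0.0115 | 0.012 | 0.122 | 0.358 |

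**And for a mean score?** The 95% half-width is t(0.975, 19)/√20 = 2.093/4.472 = 0.468 SD. That is 7.0 points for an assumed SD of 15 and 9.4 for an assumed SD of 20. A two-sided one-sample t-test would have 80% power only for a mean 0.66 SD from its reference.

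**What can leaving out early stoppers do?** Take 14 accepting patients among 20 enrolled. If the other six all complete, the completers' figure is 14/20 = 70%. If all six stop before session eight, it is 14/14 = 100%, with lower exact limit 0.025^(1/14) = 0.768. These are the two extremes. The documents give no expected dropout, so the likely effect cannot be placed between them.

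**Can the Annex 7 score be formed as printed?** Not without a rule. Simulation items 2, 5 and 8 and headset items 1 to 7 are worded negatively, 3 + 7 = 10 of the 16 items. Agreement is unfavourable on these and favourable on the other six.

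**The case against.** The best defence is that this is a pilot. Section 5.7 calls its results primarily hypothesis-generating, and sections 5.2, 5.6 and 5.8 present acceptability as something to assess rather than prove. Descriptive reporting is legitimate for that purpose. On this reading the p < 0.05 sentence is a general one, meant for outcomes that have a named test. That is probably the intention, but the text does not say so, and the absence of any benchmark remains on either reading.

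Three stronger readings are tempting, and the documents do not support them.
- A reader might infer that any score at all could be declared acceptance. Annex 7 has response columns running from disagreement to agreement, so mostly unfavourable answers would visibly contradict the hypothesis. It is the middle range that is undefined.
- A reader might infer that the cognitive comparisons are the only formal analyses left. The planned correlation and regression also cover acceptability, although they address its predictors and not its level.
- A reader might infer from section 7.1 that a loose acceptance verdict would decide whether the tool stays in use. The condition there is "if the results of the study are positive and show significant benefits for patients". It has two parts, concerns benefit, and appears as mitigation of a withdrawal effect. It does not make retention depend on acceptability alone.

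It is also fair to object that the plan defines no acceptance proportion and that 50% comes from nowhere in it. The proportions here only show how sensitive the verdict is; they are not the study's own criterion.

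**Conclusion.** The point holds. Section 5.7 states a rule that cannot be applied to the main hypothesis, and nothing in the plan separates adequate from inadequate acceptance. For the same 15 of 20 patients, the one-sided p runs from 0.0016 to 0.416 as the assumed reference moves from 40% to 70%. Sections 5.4.1 and 6.1 disagree on when the questionnaires are given, and under 5.4.1 early stoppers are lost from the main outcome.

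The contradiction and the missing reference can be read directly from the text. The sizes rest on assumed references, on acceptance being made binary, and on all 20 patients being enrolled. The direction of the early-stopper effect rests on at least some patients stopping because of VR. The defect affects how the primary result is interpreted. It does not prevent the study from running, and n = 20 is not shown to be wrong.

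**What to change.** In section 5.7:
1. Limit the p < 0.05 sentence to hypotheses that have a named test.
2. Report the Annex 7 score, with negatively worded items reversed, and the proportion of patients accepting, each with a 95% confidence interval (exact for the proportion).
3. Use all enrolled patients as the denominator for the proportion and count early stoppers as not accepting. Add a sensitivity analysis that separates withdrawals for unrelated health problems, since section 5.3 lists health problems as a reason for withdrawal.
4. Reconcile 5.4.1 with 6.1 on when the questionnaires are given, and say which administration counts.

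These steps suffice if the sponsor wants estimation only. If the report is to say that the hypothesis is supported, two things must also be fixed before data collection. One is the definition of acceptance, which should include the headset-discomfort items and the satisfaction questionnaire. The other is a justified reference that the lower 95% limit must exceed. A reference of 50%, met by at least 15 of 20, is only an example. As the table of rules shows, references of 70% or more leave little chance of success at n = 20 unless true acceptance is very high.

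The cost is a short addition to 5.7 and slightly more analysis, with no new patients, visits or questionnaire items. If a reference is set, the main hypothesis can then fail.

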4.2. Goals specific

To investigate whether VR interventions are perceived as useful and motivating by patients, which would translate into positive adherence to the cognitive stimulation program.

Measure changes in cognitive performance (particularly in attention and memory) of patients before and after the VR intervention to evaluate the effectiveness of the cognitive stimulation program.

Understand how healthcare professionals perceive VR interventions in terms of their applicability in the clinical practice of cognitive stimulation.

Identify possible improvements in the implementation of the VR program based on the comments and suggestions of patients and healthcare personnel.

Collect data and information that could be useful in developing future VR experiences for patients with cognitive impairment.

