5.2 Design

This study will be prospective and non-randomized in design. Patients will be selected from among those who already attend cognitive rehabilitation sessions at the CSSC Day Hospital. There will be no control group in this pilot study, as the primary objective is to evaluate the usability and acceptability of the intervention.

Experimental group: This group will be made up of 20 patients who attend cognitive rehabilitation sessions at the CSSC Day Hospital. These patients will participate in 8 cognitive rehabilitation sessions that will incorporate the VR experiences developed for this study.

Intervention

Sessions:

The 8 sessions will be held two days a week, at the time when the included participants have an appointment for the conventional cognitive rehabilitation program at the CSSC Day Hospital.

Equipment and Technology:

We use Oculus Quest 2 glasses and their hand tracking technology, which allows for a more immersive and less complicated experience for participants, especially those with MCI.

Developed Virtual Reality Experiences:

A) Interactive Cognitive Stimulation Exercises (Declarative Memory, Executive Functions):

Developed jointly by the BSA VR and Reality Telling teams, following the researchers' guidelines, three types of sequential interactive exercises have been created:

Step 1- Make a Purchase at the Supermarket:

- Scenario: Virtual supermarket.
- Avatar: An animated avatar greets the participant and provides instructions.
- Objective: Select ingredients to make a potato omelet or gazpacho.
- Interaction: Participants use hand tracking technology to grab products and place them in a virtual cart.
- Feedback: A success or error audio is emitted based on the product selection.

Step 2- Pay for the Purchase:

- Scenario: Checkout area of the virtual supermarket.
- Avatar: An animated avatar greets the participant and provides instructions.
- Objective: Pay the exact amount for the selected products.
- Interaction: Select 3D models of bills and coins to reach the correct sum.
- Feedback: An avatar and audio provide confirmation or correction.

Step 3- Sort the Recipe Steps:

- Scenario: Virtual kitchen.
- Avatar: An animated avatar greets the participant and provides instructions.
- Objective: Sort photos of the recipe steps.
- Interaction: Drag and drop photos into a numbered panel.
- Feedback: Confirmation of the avatar.

Scenario details:

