5.4.2 Other variables

- Age
- Sex
- Etiology of cognitive impairment
- Schooling
- Exposure to other treatments: Any additional medication or cognitive therapy that the patient is simultaneously participating in will be recorded.

5.5 Study Evaluations:

Visit	Procedures		
Selection visit (Pre-study)	Informed consent, collection of demographic data and results of cognitive function variables		
Visit 1 (Session 1)	Starting VR training sessions		
Visit 2 (Session 8 - Final)	Completion of the VR training sessions, questionnaires on cognitive function and satisfaction and usability variables.		

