5.6 Sample size

The sample size for this pilot study has been established at 20 patients. This decision is based on several factors:

Preliminary nature of the study: As this is a pilot study, the primary objective is to evaluate the usability and acceptability of the virtual reality intervention, rather than to demonstrate effectiveness. Pilot studies typically have smaller sample sizes than full studies.

Resources and capacity: The capacity of the El Carme Socio-Health Center in Badalona and the available resources (both in terms of staff and virtual reality equipment) also influence the sample size. Ensuring that each participant can receive appropriate care and support is

critical to accurate data collection and a positive patient experience.

Patient variability: Although the sample size is small, it is expected to reflect the diversity of the patient population in terms of severity of cognitive impairment, gender, age, etc. This diversity may provide a deeper understanding of how different types of patients may interact with virtual reality technology.

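### Positive adherence is part of a secondary hypothesis and a specific objective, but the plan never defines, records or analyses attendance or VR completion

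*Combined protocol and SAP*

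**What the plan says.** The second part of the claim in the first secondary hypothesis (section 3) is that VR will be valued by patients, "promoting positive adherence to the cognitive stimulation program". The first specific objective (section 4.2) asks whether patients find VR useful and motivating, "which would translate into positive adherence to the cognitive stimulation program".

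The design fixes what adherence could be measured against. Section 5.6 states "The sample size for this pilot study has been established at 20 patients". Section 5.2 states "These patients will participate in 8 cognitive rehabilitation sessions" and "The 8 sessions will be held two days a week", at the time of each patient's existing rehabilitation appointment. It also states "There will be no control group in this pilot study".

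The main outcome in section 5.4.1 is given as "Acceptability and usability of VR exercises: This will be measured using a user satisfaction questionnaire and the System Usability Scale (SUS"), collected after the eighth session. The secondary outcomes are cognitive tests and usability as judged by professionals. Section 6.1, by contrast, has patients fill in the acceptability and usability questionnaires following every session.

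**The concern.** A hypothesis needs a variable, a rule for what counts as support, and an analysis. For adherence the plan supplies none of the three. Section 4.2 treats adherence as something that follows from favourable opinion, which is the link that would have to be observed.

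Two things are at stake. First, the final report may state that adherence was good on the strength of questionnaire answers alone. Second, how many patients kept using VR, and why others stopped, is some of the most direct evidence on acceptability, which is the main objective (section 4.1). If the questionnaire is given only after the eighth session, patients who stop earlier contribute nothing to that objective, and the plan has no count of them to set beside the scores.

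**Working it through.** The sample size of 20 rests on the pilot nature of the study, resources and patient diversity. It has no formula, rate or dropout allowance, so there is no planned figure to reproduce. The check is one of tracing the adherence clause through the plan.

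| Where adherence could be made measurable | What is there | Adherence variable? |
|---|---|---|
| 5.4.1 outcomes | Satisfaction questionnaire, SUS, Digits, TMT, SDMT, MoCA, MMSE, professionals' SUS | No |
| 5.4.2 other variables | Age, sex, etiology, schooling, other treatments | No |
| 5.5 visit table | Selection visit; session 1 ("Starting VR training sessions"); session 8 with final questionnaires. Sessions 2 to 7 have no entry | No |
| 5.7 analysis | Descriptive SUS; paired tests of cognition; correlation and regression on acceptability, usability, cognition and quality of life | No |
| 6.1 data sources | Questionnaires, cognitive tests, interviews and records for age, gender, degree of impairment and other treatments | No |
| Annex 7 patient form | Opinion items, including wish to use the program often, and one item on stopping because of discomfort | No: intention and tolerability |

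Elsewhere, adherence appears only in section 7.1, as something that staff engagement may improve. No section says what would make adherence positive.

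**The two readings of questionnaire timing**
- *Section 5.4.1 (after the eighth session).* A patient who stops at, say, session 4 completes no questionnaire. Final-visit data would show who reached the end, but not how many of the 8 sessions each patient did or why others left.
- *Section 6.1 (after every session).* A form would exist for each session at which one was completed, including for patients who later stop. A missing form could mean absence, refusal of VR, a technical failure or a form not handed out. Neither section names the forms as an adherence measure.

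Clinic attendance would not settle the matter. VR is delivered inside an appointment that the patient already has, so attending does not show that VR was started or finished.

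**What the study could estimate if adherence were recorded**

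Inputs: n = 20 (5.6) and 8 sessions per patient (5.2), so 20 × 8 = 160 planned patient-sessions over 8 / 2 = 4 weeks. The number adherent, x, is assumed, because the documents give no expected value or threshold.

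The exact (Clopper-Pearson) 95% limits are the 0.025 quantile of Beta(x, n − x + 1) and the 0.975 quantile of Beta(x + 1, n − x). For x = 16 these are Beta(16, 5) and Beta(17, 4), giving 0.563 and 0.943.

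| Assumed adherent | Proportion | Exact 95% CI |
|---|---|---|
| 10/20 | 50% | 27.2% to 72.8% |
| 14/20 | 70% | 45.7% to 88.1% |
| 16/20 | 80% | 56.3% to 94.3% |
| 18/20 | 90% | 68.3% to 98.8% |
| 20/20 | 100% | 83.2% to 100% |

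At 16/20 the interval is 94.3 − 56.3 = 38.0 percentage points wide. That is enough to describe adherence and help plan a later trial, but not to support a firm claim.

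**The case against.** The strongest reply is that adherence is a trailing clause in a small, hypothesis-generating pilot. The objective itself is about perception, and Annex 7 asks patients whether they would use the program often, whether it is more entertaining than conventional exercises and whether they felt comfortable. This stands in part: the gap concerns the adherence clause, not the whole hypothesis or objective. But the clause is stated twice, and section 5.7 says that the hypotheses will be evaluated at the 5% level, so it should be measured or reworded.

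A second reply is that the study may well hold session-level information. Section 6.1 has a questionnaire at every session, section 5.2 collects participant feedback at the end of video sessions, and section 8 has side effects recorded. This also stands in part. A reader might infer that the dataset would contain nothing on adherence, that all 160 patient-sessions would go unrecorded, or that only patients reaching session 8 would ever be asked. The documents do not support those statements outright, because they depend on section 5.4.1 prevailing over section 6.1. What is established is that the two sections conflict and that neither makes the forms an adherence measure.

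A third reply is that one arm cannot show that VR promotes adherence. That is correct, and recording attendance will not change it. A reader might look for a remedy in comparing each patient with his or her own earlier attendance at conventional appointments. The documents do not support this either: section 5.3 admits only current attenders, which selects on earlier attendance, and no section shows that such attendance data are available.

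**Conclusion.** The point holds for the adherence clause. As written, the plan defines, records and analyses no attendance or completion variable, so the clause in sections 3 and 4.2 cannot be answered. The finding rests on the text and needs no assumed figure.

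The effect on the main outcome is conditional. If section 5.4.1 governs, acceptability is described only for patients who reach the eighth session. If section 6.1 governs, earlier answers exist and that problem is smaller. The documents give no dropout rate, so the size of any distortion cannot be stated.

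The gap should be corrected, but it does not undermine the study. It concerns one clause of a secondary hypothesis, and the remedy is cheap. The intervals above rest on assumed counts and show achievable precision only.

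**What to change.** 1. In 5.4.1 and the spreadsheet template of section 6.2, add for each of the 8 sessions: attended, VR started, VR completed, and the reason if not.
2. In 5.7, add a descriptive report over all enrolled patients: sessions completed out of 8 (median and range), and the proportion reaching a threshold fixed before data collection, with its exact 95% interval.
3. Reconcile 5.4.1 with 6.1 on when the questionnaires are given, and carry the result into the visit table in 5.5.
4. Reword sections 3 and 4.2 so that adherence is described, not attributed to VR. If the sponsor prefers not to record it, delete the clause.

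The cost is a few spreadsheet fields per session and one descriptive table, with no extra visit. The estimate will be imprecise with 20 patients, and the report should say so.
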